### 14.3. Other objectives

Safety and tolerability will be summarized using descriptive statistics. Adverse events will be assessed by NCI CTCAE version 4.0 criteria. The serious adverse events will be described separately.

The PFS duration will be summarized using the Kaplan-Meier method and the median PFS time will be estimated.

The treatment outcomes such as response rate and PFS will be associated with the AR expression (actual expression level, on a scale from 0-100%) by using Wilcoxon two sample test for relating to response and Cox PH model for relating to PFS.

The effect of enzalutamide (continuous) on levels of serum estradiol and testosterone and the effect on tumor AR expression by IHC will be described in graphical form and with descriptive statistics.

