### **3.0 BACKGROUND AND RATIONALE**

#### **3.1 Androgen Receptor and Ovarian Cancer**

Ovarian cancer is the second most common gynecologic malignancy and the leading cause of death among women with gynecologic malignancies. There are an estimated 21,990 new cases and 15,460 cancer-related deaths from ovarian cancer in the United States annually [1]. Approximately 75% of women with epithelial ovarian cancer present with advanced (stage III or IV) disease. Standard treatment for women presenting with advanced ovarian cancer includes cytoreductive surgery followed by combination chemotherapy with platinum and taxane agents [2]. The majority of these women will recur and be treated with multiple lines of single-agent cytotoxic chemotherapy. Progression-free survival following first, second and third remission are 10.2, 6.4 and 5.6 months respectively[3]. Long-term survival among women diagnosed with advanced-stage ovarian cancer remains < 30%. Additional options for recurrent and persistent disease are clearly needed [4, 5].

Androgen receptors (ARs) are found in 67-90% of cases of epithelial ovarian cancer, and are more prevalent than estrogen (32-55% of cases) or progesterone receptors (46-52% of cases) in this disease [6-10]. Historically, studies targeting androgen inhibition in ovarian cancer using GnRH agonists or AR antagonists have shown a response rate of 0-22% and stable disease in 8-70% of women [11-20]. Our group at MSKCC published a negative phase II study of goserelin and bicalutamide consolidation therapy in patients with 2 or more prior therapies in 2007; androgen inhibition in ovarian cancer has largely been ignored since that time [21].

However, all clinical studies of androgen inhibition in ovarian cancer to date have been performed in an unselected population of patients with multiple lines of prior treatment. Recent preclinical data shows that primary cultures of AR+ ovarian cancer cells show an increase in cell division when exposed to androgen, and that this activity is reversed when androgen is inhibited[22]. In addition, androgen receptor positivity has been shown to decrease following chemotherapy, indicating that patients with multiple lines of prior treatment may be less likely to be AR+ and therefore less likely to respond to antiandrogen therapy.

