### **3.5 Rationale for Current Study**

In summary, recent data shows that AR+ primary cultures of ovarian cancer cells proliferate in the presence of androgen and this proliferation is reversed by androgen inhibition. AR expression may be decreased following exposure to multiple lines of cytotoxic chemotherapy. Abiraterone acetate has shown promising results in patients with

AR+ breast cancer; however due to suppression of adrenally produced androgen it can produce severe side effects related to hypokalemia, hypertension and edema. In the ovarian cancer population, where malignant ascites is common, toxicities related to increased edema from abiraterone and prednisone would be significant.

Prior targeted therapies for treatment of ovarian cancer have shown response rates of 0%-21% and PFS at 6 months of 6.5%-40.3% in patients with recurrent or advanced ovarian cancer and a history of 1-2 prior cytotoxic therapies (Table 1).

Table 1.

Study	Agent	Target	N	Response Rate	PFS at 6 Months
170-C	Gefitinib	EGFR	27	3.7%	14.8%
170-D	Bevacizumab	VEGFA	62	21%	40.3%
170-E	Imatinib	Bcr-abl/c-kit/PDGFR	56	1.8%	16.1%
170-F	Sorafenib	VEGFR/PDGRR/RAF	59	3.4%	23.7%
170-G	Lapatinib	EGRR/HER2neu	26	0.0%	7.7%
170-H	Vorinostat	HDAC	27	3.7%	7.4%
170-J	Enzastaurin	PKC-beta	27	7.4%	11.1%
170-K	Mifepristone	PR	22	4.5%	13.6%
170-M	Dasatinib	Scr/bcl-abl/c-kit	34	0%	20.6%
170-N	A6	uPAR	31	0%	20.6%
170-P	AMG-102	HGF(c-met)	Suspended after first stage		

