## 4.1 OVERVIEW OF STUDY DESIGN/INTERVENTION

### 4.2 Design

This is a single-institution, single-arm, open-label, phase II study of enzalutamide 160mg by mouth once daily in patients with AR+ recurrent or advanced ovarian, primary peritoneal or fallopian tube cancer. After signing a screening consent, patients archival tissue will be evaluated for degree of AR positivity by AR staining. Patients with no archival tissue available will undergo a biopsy (using the modality deemed most appropriate by the patient's physician) for collection of tumor tissue for AR positivity by IHC. Only AR+ patients, defined as  $\geq 5\%$  positivity by IHC, will be included. All IHC testing will be performed in the MSKCC Clinical CLIA approved laboratory.

All eligible patients will have measurable disease by RECIST 1.1 criteria and will have received one, two or three prior cytotoxic treatments for their disease. A maximum of 19 enrolled patients will have 3 prior therapies. Patients will be treated until POD, intolerable toxicity or withdrawal of consent.

The primary endpoint of this trial is to determine the proportion of women with AR(+) ovarian, primary peritoneal, or fallopian tube cancer who survive progression free for at least 6 months and the proportion of patients who have objective tumor response (complete or partial response) by RECIST 1.1 criteria when treated with enzalutamide 160mg PO QD.

The frequency and severity of adverse events as assessed by NCI CTCAE version 4.0 will be described. Optional tumor biopsies will be performed at end of treatment, in order to explore the effect of enzalutamide on tumor AR expression.

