## 10.2 Correlative Studies

The degree of nuclear AR expression levels will be determined using standard immunohistochemistry methodology on all tissue and reported as percent tumor cells with nuclear AR staining. One-three 5 micrometer superplus frost slides will be used for IHC testing. This testing will be performed at the Memorial Sloan-Kettering Cancer Center CLIA approved Clinical Laboratory using the Dako androgen receptor antibody. Upon receipt of the slide in the clinical laboratory, results will be reported within 48 hours. The relationship between tumor response and degree of AR expression, and/or AR signaling, will be examined. Additional assays for AR signaling, (e.g., gene expression array analyses, mutation analyses, or other immunohistochemistry evaluations) may be performed on remaining tissue to evaluate for molecular phenotypes and patterns associated with activated AR signaling.

Germline DNA will be used both for cell free DNA analysis and as a matched normal for MiSeq analysis. MiSeq will be used to evaluate for alterations within the androgen, estrogen, and progesterone receptors. Germline DNA from peripheral blood will be used to filter out germline variants. The germline DNA sequencing data will be used as a filter to define somatic alterations and will not be reported. A 10cc tube of whole blood will be collected on Cycle 1, Day 1 and on Cycle 2, Day 1 for use in gene expression analyses. This testing will be performed at Memorial Sloan-Kettering Cancer Center.

Archived patient blood and/or tissue may be sent to Medivation Inc. and/or Astellas for additional analyses.

Any additional future studies performed using the clinical information, blood, or tissue collected from this study will only be performed after completion of appropriate institutional approval.

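### The exploratory AR analyses in 14.3 should account for number of prior cytotoxic regimens, which the protocol itself links to both AR expression and PFS

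*Combined protocol and SAP*

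**What the plan says.** Section 14.3 (Other objectives) relates response and PFS to AR expression, taken as the "actual expression level, on a scale from 0-100" percent, "by using Wilcoxon two sample test for relating to response and Cox PH model for relating to PFS". It names no covariate, stratum or sensitivity analysis. Section 10.2 (Correlative Studies) raises the same question, again without adjustment: "The relationship between tumor response and degree of AR expression, and/or AR signaling, will be examined".

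Three other statements bear on this.

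- **Prior treatment and AR.** Section 3.1 says "androgen receptor positivity has been shown to decrease following chemotherapy", and infers that heavily pretreated women may be less likely to be AR+. Section 3.5 is more guarded: "AR expression may be decreased following exposure to multiple lines of cytotoxic chemotherapy".
- **Prior treatment and PFS.** Section 3.1: "Progression-free survival following first, second and third remission are 10.2, 6.4 and 5.6 months respectively".
- **Spread of prior treatment in the sample.** Under section 4.2, patients "will have received one, two or three prior cytotoxic treatments for their disease", and "A maximum of 19 enrolled patients will have 3 prior therapies". Section 4.3 caps the three-prior group at 9 of the 28 stage I patients.

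The caps and the eligibility criteria mean that the number of prior regimens must be known for every patient.

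**The concern.** A variable linked to both AR and PFS can create an association between them. If women with fewer prior regimens tend to have higher AR and longer PFS, then higher AR will accompany longer PFS even when AR has no bearing on outcome. The two-sample Wilcoxon test is unadjusted by construction. For the Cox model, the absence of adjustment is inferred from the plan naming AR as the only explanatory variable.

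AR selection is the premise of the study (section 3.5), and these are the only planned analyses of whether outcome varies with AR level among the women selected. An artefact of treatment line would run in the direction that makes AR look favourable.

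**Working it through.** The plan gives no sample size, power or alpha for the AR analyses, so it has no figure to reproduce. The question is how often a Cox model on AR alone would reject at 5% if AR had no effect.

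**Inputs from the documents**

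- PFS by line: 10.2, 6.4 and 5.6 months (section 3.1). With exponential times, the hazard ratios against the first are 10.2/6.4 = 1.59 and 10.2/5.6 = 1.82.
- Sample size: 59 (section 14.2, sample size). Sections 4.3 and 14.2 also use 30 stage II patients, which gives 58; the difference is immaterial here.
- At most 19 patients with three prior therapies, hence a split of 20/20/19.
- Null 6-month PFS 15%; response 5% (null) to 20% (target).

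**Assumptions, not in the documents**

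- AR falls by 10 or 20 points per line: AR = 60 − fall × (prior regimens − 1) + Normal(0, SD 25), limited to 5–100.
- The section 3.1 PFS figures are medians, and first, second and third remission map to one, two and three prior regimens.
- Follow-up is cut at 12 months.

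**PFS settings**

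- A: the section 3.1 medians as given.
- B: the same ratios scaled to a first median of 3 months, that is 3.00, 3 × 6.4/10.2 = 1.88 and 3 × 5.6/10.2 = 1.65. Since 6-month PFS is 2^(−6/median), these give 25%, 11% and 8%. The average is (20 × 0.25 + 20 × 0.110 + 19 × 0.080)/59 = 14.8%, which matches the design's null of 15%.
- C: a nearly flat gradient of 6.4, 5.6 and 5.6 months.

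**Results**: 4,000 simulated trials per row with no AR effect, all AR tissue reflecting the current line, Wald test at two-sided 5%. The simulation error is about √(0.06 × 0.94/4000) = 0.4 points at 6%. HR per SD is the average spurious hazard ratio for AR from the AR-alone model.

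| PFS setting | AR fall per line | AR alone | AR + prior regimens | HR per SD of AR |
|---|---|---|---|---|
| A | 0 | 5.2% | 5.8% | 1.00 |
| A | 10 | 7.2% | 5.7% | 0.92 |
| A | 20 | 13.6% | 6.2% | 0.87 |
| B | 10 | 8.8% | 6.0% | 0.92 |
| B | 20 | 16.5% | 6.0% | 0.87 |
| C | 10 | 5.5% | 5.7% | 0.98 |
| C | 20 | 5.7% | 6.3% | 0.97 |

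**Tissue timing.** If half the specimens predate the later lines, AR alone rejects in 5.8–7.3% (A) and 7.0–7.8% (B). If 75% do, the rates are 5.0–6.0% (A) and 5.4–6.0% (B), no higher than with adjustment.

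**Response.** With assumed response rates of 18%, 12% and 6% by line and AR falls of 0.25 to 1.0 SD per line, the plain Wilcoxon test rejects in about 5–12%. Expected responders are 59 × 0.05 = 3 to 59 × 0.20 = 12. A stratum without a responder adds nothing to a stratified test. At 20%, 12% and 6% by line, the chance of at least one such stratum is 1 − (1 − 0.80^20)(1 − 0.88^20)(1 − 0.94^19) = 37%. At 5% throughout it is 1 − (1 − 0.95^20)²(1 − 0.95^19) = 74%.

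**The case against.** There are five serious points on the other side.

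- **The link to AR is uncertain and its size unknown.** The effect of multiple lines is stated with a may. Section 3.1 speaks of positivity, whereas the trial enrols only tumours with at least 5% staining, and no gradient in percentage among those is given. This stands: the assumed fall drives the result.
- **Archival tissue is the default.** A biopsy is taken only when no archival tissue is available (sections 4.2, 4.3 and 10.1.b), and tissue taken before chemotherapy cannot have been lowered by later regimens. This stands, and could remove the excess. But the plan neither requires pre-chemotherapy tissue nor states a collection date, and women biopsied at screening are sampled after all their prior lines.
- **The PFS gradient may be flatter here.** Section 6.2 restricts only one-prior women to a platinum-free interval under 12 months, or to progression on or persistence after platinum. That selects a poorer-prognosis group. This also stands, and setting C shows the consequence.
- **Nothing is decided by these analyses.** They carry no alpha and no decision rule. A reader might infer that they would settle AR selection in a later trial; the documents do not say so.
- **A stratified test is fragile with few responders.** This stands, and limits the response remedy to a sensitivity analysis.

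A reader might also apply the 1.59 ratio at both steps, which gives rejection rates as high as 28%. That implies a hazard ratio of 1.59² = 2.53 for three against one prior regimen, or a median of 10.2/2.53 = 4.0 months. Section 3.1 gives 5.6 months, so the documents do not support that figure.

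**Conclusion.** The concern holds as a modest weakness in an exploratory analysis. On the protocol's own account, number of prior regimens is linked to AR and to PFS, yet the AR analyses leave it out. With section 3.1's PFS ratios and an assumed AR fall of 10 to 20 points per line, the false-positive rate of the Cox test is roughly 7–17% unadjusted and about 6% adjusted. The excess largely disappears if most AR tissue predates the later lines or if the gradient is nearly flat. Which case applies cannot be known in advance, which is the reason to specify the adjustment now.

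Two stronger readings are not supported. The documents do not show that AR will look favourable for this reason, only that it could. Nor would adjustment make the analysis a test of prediction: with no control arm, neither model can separate a predictive from a prognostic role for AR. The primary endpoints and their decision rule are untouched.

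**What to change.** In section 14.3:

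- **PFS.** Fit the Cox model with AR percentage plus number of prior cytotoxic regimens (1, 2, 3), and report it beside the model with AR alone.
- **Response.** Keep the Wilcoxon test and add a version stratified by prior regimens (van Elteren) as a sensitivity analysis, not as the main result, given the 3 to 12 responders expected.
- **Labelling.** State that these analyses are exploratory, that without a control arm they cannot show AR to be predictive rather than prognostic, and that they do not bear on the primary decision rule.

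The cost is a few sentences of text and a few lines of code, using a variable that eligibility already requires. Statistically it is one degree of freedom if prior regimens enters as a linear term and two if it enters as categories. In the simulation both forms held rejection at about 6%. Recording whether each AR specimen predates the later regimens would help readers judge how much confounding was possible.

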Target lesions. All measurable lesions up to a maximum of 2 lesions per organ and 5 lesions in total, representative of all involved organs, should be identified as **target lesions** and recorded and measured at baseline. Target lesions should be selected on the basis of their size (lesions with the longest diameter), be representative of all involved organs, but in addition should be those that lend themselves to reproducible repeated measurements. It may be the case that, on occasion, the largest lesion does not lend itself to reproducible measurement in which circumstance the next largest lesion which can be measured reproducibly should be selected. A sum of the diameters (longest for non-nodal lesions, short axis for nodal lesions) for all target lesions will be calculated and reported as the baseline sum diameters. If lymph nodes are to be included in the sum, then only the short axis is added into the sum. The baseline sum diameters will be used as reference to further characterize any objective tumor regression in the measurable dimension of the disease.

Non-target lesions. All other lesions (or sites of disease) including any measurable lesions over and above the 5 target lesions should be identified as **non-target lesions** and should also be recorded at baseline. Measurements of these lesions are not required, but the presence, absence, or in rare cases unequivocal progression of each should be noted throughout follow-up.

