#### 14.2. Sample size calculation for the two-stage phase II trial

Prior targeted therapies for treatment of ovarian, primary peritoneal, and fallopian tube cancer have shown response rates of 0%-21% and PFS at 6 months of 6.5%-40.3% in patients with recurrent or advanced ovarian, primary peritoneal, or fallopian tube cancer and a history of 1-2 prior cytotoxic therapies. We hypothesize that treatment with enzalutamide will result in an increase in tumor response rate from 5% to 20% or an increase in 6-month PFS rate from 15% to 30% ( $H_0: \pi_r \leq 0.05$  and  $\pi_{pfs} \leq 0.15$  vs.  $H_1: \pi_r > 0.05$  or  $\pi_{pfs} > 0.15$ ). To test the null hypotheses in a two-stage design, a method provided by Sill and Yothers [32] is used. In particular, in stage I, 28 eligible patients will be evaluated, if 3 or more patients have clinical response or 5 or more patients have no progression/death at 6 months, then the study will open to the second stage accrual. In

stage II, an additional 31 patients will be enrolled. At the end of stage II, if at least 7 of 59 (28+31=59) patients have clinical response or at least 13 of 59 patients survive progression free for 6 months, this will be considered as a positive trial.

Assuming the two primary endpoints are independent, the power in each scenario and the type 1 error are listed as in the following table:

		PFS rate at 6mo	
		$\pi_{pfs} = 0.3$	$\pi_{pfs} = 0.15$
Response	$\pi_{rr} = 0.20$	0.99	0.94
	$\pi_{rr} = 0.05$	0.90	0.10

Assuming the two primary endpoints are highly correlated (as the joint probability of  $\pi_{rr}$  and  $\pi_{pfs}$  is  $0.90 \times \min(\pi_{rr}, \pi_{pfs})$  [32]), the power in each scenario and the type 1 error are as the following:

		PFS rate at 6mo	
		$\pi_{pfs} = 0.3$	$\pi_{pfs} = 0.15$
Response	$\pi_{rr} = 0.20$	0.97	0.92
	$\pi_{rr} = 0.05$	0.90	0.09

When the null hypotheses are true for both the response and the PFS, the chance of stopping the trial after stage I enrollment is 49% under independence and 55% under dependence.

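### The AR-response test compares about 3 to 12 responders with everyone else; adding a rank correlation of AR with tumor-size change would use data already collected, at almost no cost

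*Combined protocol and SAP*

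**What the plan says.** Section 14.3 states: "The treatment outcomes such as response rate and PFS will be associated with the AR expression", with AR taken as the "actual expression level, on a scale from 0-100" percent. The methods are given in one clause: "by using Wilcoxon two sample test for relating to response", and a Cox model for PFS. No significance level, effect size or power is attached to either method. Section 10.2 gives the purpose: "The relationship between tumor response and degree of AR expression, and/or AR signaling, will be examined". This association is not among the objectives in section 2.1.

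The size measurements are already part of the trial. Sections 4.2 and 6.2 require measurable disease in every patient. Section 12.2 (Disease Parameters) says: "A sum of the diameters (longest for non-nodal lesions, short axis for nodal lesions) for all target lesions will be calculated". Section 4.3 schedules imaging every 8 weeks, and section 12.41 defines partial response and progression from that same sum. No analysis of percent change in the sum is planned.

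**The concern.** The Wilcoxon test reduces a continuous measurement to yes or no at the 30% shrinkage cut, and then compares a very small group with a large one. If AR level is moderately related to shrinkage, the test will usually miss it. At a low response rate it may have no responder to compare. Section 3.5 presents AR-selected enrollment as what separates this trial from earlier unselected studies, so a null result here could be misread as showing that the degree of AR expression is irrelevant. Percent change in the target-lesion sum exists for every patient with a post-baseline scan and would carry more information.

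**Working it through.** **Plan's own figures.** Section 14.3 gives no power to reproduce. The design figures in section 14.2 were recomputed by exact enumeration of the joint response and 6-month PFS counts over both stages. With 28 + 30 = 58 patients, power is 0.99, 0.94 and 0.905 and type I error 0.099 under independence; under dependence, 0.97, 0.92, 0.90 and 0.090. Early stopping under the null is 49% and 55%. These match. Section 14.2 also gives stage II as 31 (total 59), against 30 in section 4.3 and in the accrual paragraph of 14.2; with 59 the type I errors become 0.109 and 0.099. Those passages need reconciling separately. The difference barely moves the responder counts below.

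**Responders expected.** Rates are 5% and 20% (section 14.2) and 12.5% (section 3.5).
- 58 patients: 58 × 0.05 = 2.9; 58 × 0.125 = 7.25; 58 × 0.20 = 11.6.
- 28 patients, if the trial stops: 28 × 0.05 = 1.4; 28 × 0.20 = 5.6.
- Chance of no responder at 5%: 0.95^58 = 0.05 and 0.95^28 = 0.24.

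**Model (assumed).** AR and shrinkage are bivariate normal with correlation r. Responders are the patients with the greatest shrinkage, at the stated rate. Tests are two-sided at 5%. Power is by simulation.

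**Power, 58 patients, r = 0.4**

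| Analysis | 5% response | 12.5% | 20% |
|---|---|---|---|
| Wilcoxon, as planned | 0.25 | 0.44 | 0.56 |

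| Spearman, by handling of unscanned patients | Power, range over the three rates |
|---|---|
| 6-12 excluded, or worst-ranked and truly in the worse half | 0.76-0.82 |
| 6 worst-ranked, missingness unrelated to AR | 0.70-0.75 |
| 12 worst-ranked, missingness unrelated to AR | 0.51-0.61 |

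The last two rows draw the unscanned patients from non-responders, since a responder must have been scanned. Drawing them from all patients gives about 0.65 (6) and 0.44 (12). Type I error was 0.03-0.06 for all versions.

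**Other correlations** (3, 7 or 12 responders of 59; Spearman on 50-59 evaluable patients, the rest excluded)

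| r | Wilcoxon | Spearman |
|---|---|---|
| 0.2 | 9%, 14%, 18% | 28-31% |
| 0.3 | 17%, 26%, 34% | 52-60% |
| 0.5 | 41%, 65%, 78% | 95-97% |

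**Stop at 28 patients, r = 0.4, about 10% unscanned.** Wilcoxon 0.08-0.28; Spearman 0.36-0.49.

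**The Cox model.** Power = Φ(√D × |ln HR per SD| − 1.96), with D = 50 PFS events assumed.
- HR 0.80: 7.07 × 0.223 − 1.96 = −0.38, power 35%.
- HR 0.70: 7.07 × 0.357 − 1.96 = 0.56, power 71%.
- HR 0.60: 7.07 × 0.511 − 1.96 = 1.65, power 95%.

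**The case against.** Five points can be made for the plan.

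- A reader might infer that the AR analysis as a whole has little power. The documents do not support that. The Cox model uses AR and PFS in full and has moderate to good power for strong effects. This stands; the weakness is confined to the response half. The Cox model, however, addresses PFS and not the tumor-response question of section 10.2.
- A reader might also infer that the analysis is meant to validate AR as the selection marker. No section says so. Section 10.2 only promises an examination, section 2.1 does not list it, and no decision rule depends on it. Since only tumors with at least 5% AR staining enroll, neither test can examine the cut-off. This stands.
- Response is a primary endpoint and takes in new lesions, non-target lesions and confirmation (sections 12.42 and 12.43). Percent change in target lesions ignores all three, so a patient with shrinking targets and a new lesion would look favorable. This stands, and it rules out replacing the response comparison.
- The Wilcoxon test is not weak everywhere: with 12 responders and a 1.0 SD difference in AR its power is 84%. True, but at 0.8 SD it is 24%, 46% and 65% with 3, 7 and 12 responders.
- The gain depends on who is unscanned. With 12 patients worst-ranked and missingness unrelated to AR, the Spearman advantage at 20% response is small or absent. This stands as a limit on the size of the gain, and is why an analysis excluding those patients is needed too.

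**Conclusion.** The point holds as a low-cost improvement to an exploratory analysis. The planned response comparison rests on about 3 to 12 responders, and fewer if the trial stops at 28. At an assumed correlation of 0.4 it detects the association in roughly a quarter to just over half of full-size trials. The continuous analysis reaches about 0.76-0.82 in the favorable missing-data cases and 0.51-0.75 in the less favorable ones. At 28 patients both are underpowered, and at 5% response about a quarter of such trials cannot run the Wilcoxon test at all.

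The correlations, the numbers unscanned and the 5% two-sided level are assumptions; the documents give none of them. The gain also presumes that AR relates to size change across its range. At a correlation of 0.2 neither analysis is informative. The primary endpoints and their error rates are unaffected.

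**What to change.** In section 14.3, keep the Wilcoxon and Cox analyses and add a third: a Spearman correlation of baseline AR percent with best percent change from baseline in the sum of target-lesion diameters. Give the worst rank to patients who progress or die without a post-baseline scan, and add a sensitivity analysis that excludes them. State that the analysis is exploratory, that it supplements the RECIST response comparison, and that it does not test the 5% AR cut-off. Report how many patients had no post-baseline scan.

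The cost is two or three sentences and no new data. The definition of percent change and the worst-rank rule should be fixed before outcomes are examined, because several definitions are possible. The drawback is a second AR-response result that ignores new lesions, non-target lesions and confirmation, and so has to be read beside the response comparison.
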